1. BACKGROUND AND RATIONALE

Critically ill patients in the intensive care unit (ICU) experience a high degree of physiological stress and catabolism. This results in rapid muscle breakdown and deconditioning, resulting in prolonged functional disability which persists even after the critical illness. To minimize this, it is important that patients are given adequate nutrition and physical therapy during the period of critical illness.

Currently, our surgical ICU (SICU) patients receive feeding based on a weight-based empiric formula (25 kcal/kg/day). This method of estimating caloric requirement is inaccurate in underweight, overweight and oedematous patients. In our study, we will be examining the use of indirect calorimetry, which is the gold standard for assessing energy requirements. Studies done on indirect calorimetry directed feeding have not shown a significant impact on functional outcome. We hypothesize that the patients included in these studies may not have received adequate physical therapy.

With regards to physical therapy, our SICU patients receive regular standard physiotherapy sessions. Studies have shown that physical therapy in the critically ill improves functional outcome only marginally. We hypothesize that the marginal result could be due to inadequate feeding of the patients studied. In our study, we will be examining the use of cycle ergometry. Cycle ergometry has been shown to be safe and feasible in critical care patients, however there have been no studies examining its effect on functional outcome.

We hypothesize that indirect calorimetry directed nutritional support in combination with enhanced physical therapy using cycle ergometry synergistically improves functional outcome of critically ill patients.

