1.2. Rationale and justification for the Study

We hypothesize that indirect calorimetry directed feeding in combination with enhanced physical therapy using cycle ergometry synergistically improves functional outcome of critically ill patients.

We are conducting this study in the hope to eventually improve functional outcomes in critically ill patients, particularly the elderly population as they have low reserves to start with. The burden of disability among the patients discharged from the ICU is increasing due to our aging population.

a. Rationale for the Study Purpose

Critically ill patients in the intensive care unit (ICU) experience a high degree of physiological stress and catabolism. This results in rapid muscle breakdown and deconditioning, resulting in prolonged functional disability which persists even after the critical illness. To minimize this, it is important that patients are given adequate nutrition and physical therapy during the period of critical illness.

Currently, our surgical ICU (SICU) patients receive feeding based on a weight-based empiric formula (25 kcal/kg/day). This method of estimating caloric requirement is inaccurate in underweight, overweight and oedematous patients. In our study, we will be examining the use of indirect calorimetry, which is the gold standard for assessing energy requirements. Studies done on indirect calorimetry directed feeding have not shown a significant impact on functional outcome. We hypothesize that the patients included in these studies may not have received adequate physical therapy.

With regards to physical therapy, our SICU patients receive regular standard physiotherapy sessions. Studies have shown that physical therapy in the critically ill improves functional outcome only marginally. We hypothesize that the marginal result could be due to inadequate feeding of the patients studied. In our study, we will be examining the use of cycle ergometry. Cycle ergometry has been shown to be safe and feasible in critical care patients, however there have been no studies examining its effect on functional outcome.

We hypothesize that indirect calorimetry directed feeding in combination with enhanced physical therapy using cycle ergometry synergistically improves functional outcome of critically ill patients.

b. Rationale for Study Population

We are conducting this study in the hope to eventually improve functional outcomes in

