critically ill patients, particularly the elderly population as they have low reserves to start with. The burden of disability among the patients discharged from the ICU is increasing due to our aging population.

c. Rationale for Study Design

We will be conducting a randomized controlled trial as it is most suitable to answer our clinical question.

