2. HYPOTHESIS AND OBJECTIVES

2.1. Hypothesis

Feeding by indirect calorimetry and early exercise with cycle ergometry will reduce muscle mass loss in the older critical ill patient and improve functional outcomes.

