2.2. Primary Objectives

Adequate feeding and early exercise by cycle ergometry will reduce muscle mass loss as estimated by quadriceps muscle ultrasound

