3. STUDY POPULATION

3.1. List the number of subjects to be enrolled.

50 patients - 25 study subjects in Group A - Intervention arm, 25 study subjects in Group B
- Control arm

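### Does a two-arm comparison of the package with usual care conflict with a rationale that speaks of synergy between feeding and cycling?

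*Protocol*

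**What the plan says.** The synergy wording appears three times, all in the rationale: once in section 1 and twice in section 1.2. Section 1 hypothesises that calorimetry-directed nutritional support "in combination with enhanced physical therapy using cycle ergometry synergistically improves functional outcome of critically ill patients". The sentence in 1.2 reads: "We hypothesize that indirect calorimetry directed feeding in combination with enhanced physical therapy using cycle ergometry synergistically improves functional outcome of critically ill patients". Around it, both sections suggest that earlier feeding studies may have failed for want of physical therapy, and that earlier physical therapy studies may have shown little for want of feeding. Section 1.2 c adds: "We will be conducting a randomized controlled trial as it is most suitable to answer our clinical question".

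The operative sections are worded differently. The hypothesis in 2.1 is: "Feeding by indirect calorimetry and early exercise with cycle ergometry will reduce muscle mass loss in the older critical ill patient and improve functional outcomes". The primary objective in 2.2 is: "Adequate feeding and early exercise by cycle ergometry will reduce muscle mass loss as estimated by quadriceps muscle ultrasound". Section 2.3 lists the functional scores CPAx and FSS-ICU among the secondary outcomes.

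On structure, section 3.1 gives "50 patients - 25 study subjects in Group A - Intervention arm, 25 study subjects in Group B" as control. Section 4 assigns calorimetry-titrated feeding together with cycling to Group A, and standard nutrition with standard physiotherapy to Group B. Nobody is randomised to one component alone. Section 9.1 calls the study a pilot because the combination has not been studied before, and gives 21 per arm for 80% power, raised to 25 for drop-outs.

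**The concern.** To a statistician, synergy is a claim about interaction: that the two components together do more than the sum of what each does alone. The argument in the rationale, that each treatment has underperformed because the other was missing, is also a claim that one effect depends on the other. A trial of both against neither cannot test it. A positive result would fit a pure feeding effect, a pure cycling effect, simple addition, synergy or even mild antagonism.

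If synergy were the question of the trial, the design would be wrong for it, and no statistical analysis plan could repair that, because the limit lies in the arms. There is also a practical risk. Calorimetry and cycling are separate resources, and a unit reading the report might want to adopt only one. Finally, the rationale puts function first while the primary objective is muscle loss, which can look like two competing hypotheses in one document.

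**Working it through.** **1. The plan's own figure.** Section 9.1 gives 21 per arm, power 0.80 and a 25% reduction in muscle thickness. It gives no SD, significance level or sidedness, so 21 can be neither confirmed nor refuted. Assume two-sided 0.05 and the normal approximation, n per arm = 2 × ((1.960 + 0.842)/d)²:

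- d = √(2/21) × 2.802 = 0.865.
- Reading the 25% as a 25-point difference between arms, the implied SD is 25/0.865 = 28.9 points.
- At one-sided 0.05 the implied SD would be about 32.6 points.
- The step from 21 to 25 corresponds to 16% drop-out: 21/(1 − 0.16) = 25.

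This calculation is for the contrast of Group A with Group B, which is the contrast the two arms supply.

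**2. What two arms can identify.** Write each group mean as baseline + feeding effect + cycling effect + interaction.

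- Group B observes the baseline.
- Group A observes the baseline plus all three effects.
- There are two equations for four unknowns (rank 2 of 4). Only the sum feeding + cycling + interaction can be estimated.

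With the 25-point difference for illustration:

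| Feeding | Cycling | Interaction | A − B |
|---|---|---|---|
| 25 | 0 | 0 | 25 |
| 0 | 25 | 0 | 25 |
| 12.5 | 12.5 | 0 | 25 |
| 5 | 5 | 15 | 25 |
| 15 | 15 | −5 | 25 |

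Not even the sign of the interaction is determined. The technical claim therefore holds.

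**3. What it would cost to identify it.** In a 2×2 factorial the interaction contrast has variance 4 × SD²/n per cell, so n per cell = 4 × ((1.960 + 0.842)/D)², where D is the standardised interaction.

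- D equal to the whole package effect (0.865): 42 per cell, 168 in total. That is 2 × 21 per cell, so this ratio does not depend on the assumed significance level or SD. With 16% drop-out it is 42/0.84 = 50 per cell, 200 in total.
- D half of it: 168 per cell, 672 in total.
- D a quarter of it: 672 per cell, 2,688 in total.
- The planned 50 patients spread over four cells (12.5 each) would give power of about 33%, 12% and 6% in these three cases, at two-sided 0.05.

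**4. Where the word matters.** Going through the sections in turn:

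- 1 and 1.2 use the word, as the reason for combining the treatments.
- 1.2 c defends randomisation. It mentions neither synergy nor the number of arms, so it is not a claim that two arms can show synergy.
- 2.1, 2.2, 2.3, 5.1 and 9.1 do not use it. They are framed around feeding plus cycling.

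**5. Function against muscle.** Section 2.1 names both: muscle loss first, then functional outcomes. Section 2.2 makes muscle loss primary and 2.3 makes the functional scores secondary. That is an ordering of endpoints and does not set up two hypotheses.

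**The case for a change.** The strongest case for a change is that this is more than a stray adverb. It appears three times, each time in a sentence that begins as a hypothesis, and the surrounding argument is one of effect modification. Sections 1 and 1.2 also say that the study will examine calorimetry and will examine cycling, which may lead a reader to expect an answer on each. The remedy would be cheap: wording only, with no added patients or procedures.

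The part that stands is the limit on inference. No statement about synergy, or about either component alone, can be drawn from these data, and anyone reporting the trial should keep to the package.

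The part that does not stand is the inference that the plan is set up to make such a claim. No objective, endpoint or sample size statement refers to synergy, and section 11 says only that the outcomes will be published. The rationale can fairly be read as the biological reason for testing the two together, although its phrasing as a hypothesis makes that reading less than perfect. Rewriting those sentences around muscle loss alone would also create a mismatch, because it would take out the functional outcome that 2.1 keeps.

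**Conclusion.** No change to the plan follows. The synergy contrast cannot be identified from two arms, and that is certain from the arm structure alone. But synergy is the motive for the combination and is not the hypothesis under test. Following the Protocol as written yields a comparison of the package with usual care, which is what 2.1 and 2.2 ask for and what the 21 per arm in 9.1 was computed for. Testing a new combination as a whole before taking it apart is a fair trade-off in a pilot of 50, given that a factorial would need at least about 168 evaluable patients in the most favourable of the cases examined.

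Dropping the adverb would tidy the rationale but would move no arm, endpoint, estimate, error rate or stated figure. The factorial sizes assume power 0.80, a common SD and an interaction expressed as a share of the back-solved package effect. The power figures for 50 patients also assume two-sided 0.05. The conclusion does not depend on any of these numbers.

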1.1. General Introduction

Indirect calorimetry is the gold standard for assessing energy requirements. It involves measuring the amount of oxygen consumed by the patient and the amount of carbon dioxide produced by the patient. Using the Weir formula, the energy expenditure of the patient can be calculated. Although indirect calorimetry is considered the gold standard, it is not routinely used in the SICU.

Cycle ergometry enables active and passive cycling in bed bound patients. It has been mainly used in the outpatient rehabilitation setting. It has been shown to be feasible and safe to be used in the ICU setting. However, there are no studies examining its effectiveness in improving functional outcome in critical care patients.

1.2. Rationale and justification for the Study

We hypothesize that indirect calorimetry directed feeding in combination with enhanced physical therapy using cycle ergometry synergistically improves functional outcome of critically ill patients.

We are conducting this study in the hope to eventually improve functional outcomes in critically ill patients, particularly the elderly population as they have low reserves to start with. The burden of disability among the patients discharged from the ICU is increasing due to our aging population.

a. Rationale for the Study Purpose

Critically ill patients in the intensive care unit (ICU) experience a high degree of physiological stress and catabolism. This results in rapid muscle breakdown and deconditioning, resulting in prolonged functional disability which persists even after the critical illness. To minimize this, it is important that patients are given adequate nutrition and physical therapy during the period of critical illness.

Currently, our surgical ICU (SICU) patients receive feeding based on a weight-based empiric formula (25 kcal/kg/day). This method of estimating caloric requirement is inaccurate in underweight, overweight and oedematous patients. In our study, we will be examining the use of indirect calorimetry, which is the gold standard for assessing energy requirements. Studies done on indirect calorimetry directed feeding have not shown a significant impact on functional outcome. We hypothesize that the patients included in these studies may not have received adequate physical therapy.

With regards to physical therapy, our SICU patients receive regular standard physiotherapy sessions. Studies have shown that physical therapy in the critically ill improves functional outcome only marginally. We hypothesize that the marginal result could be due to inadequate feeding of the patients studied. In our study, we will be examining the use of cycle ergometry. Cycle ergometry has been shown to be safe and feasible in critical care patients, however there have been no studies examining its effect on functional outcome.

We hypothesize that indirect calorimetry directed feeding in combination with enhanced physical therapy using cycle ergometry synergistically improves functional outcome of critically ill patients.

b. Rationale for Study Population

We are conducting this study in the hope to eventually improve functional outcomes in

critically ill patients, particularly the elderly population as they have low reserves to start with. The burden of disability among the patients discharged from the ICU is increasing due to our aging population.

c. Rationale for Study Design

We will be conducting a randomized controlled trial as it is most suitable to answer our clinical question.

2. HYPOTHESIS AND OBJECTIVES

2.1. Hypothesis

Feeding by indirect calorimetry and early exercise with cycle ergometry will reduce muscle mass loss in the older critical ill patient and improve functional outcomes.

2.2. Primary Objectives

Adequate feeding and early exercise by cycle ergometry will reduce muscle mass loss as estimated by quadriceps muscle ultrasound

2.3. Secondary Objectives

The secondary outcomes are 1) ICU mortality 2) ICU and hospital length of stay 3) functional assessments of mobility such as Chelsea Critical Care Physical Assessment Tool (CPAx) and Functional Status Score for the ICU (FSS-ICU). 4) Assessment of strength i.e Handgrip Strength using dynamometer and Medical Research Council Sum Score (MRC-SS).

2.4. Potential Risks and benefits:

a. End Points - Efficacy

We would expect patients who undergo early exercise and feeding have improved functional outcomes, mobilise earlier and avoid problems of prolonged hospital stay. This would avoid the severe problems of deconditioning and muscle loss in the older patient.

b. End Points - Safety

Patients might have some mild cardiovascular instability as with any exercise regimen and hence the strict temporary exclusion criteria before the commencement of the exercise. Patients are closely monitored on ICU and any deviation from baseline parameters will lead to the termination of the exercise cycle ergometry. Other ICU studies have showed the

safety of the cycle ergometry in this group of ICU patients.

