4. STUDY SCHEDULE

Patients recruited and randomised to Group A (intervention), will undergo daily indirect calorimetry to obtain their resting energy expenditure (REE), have their enteral feeds titrated to the REE, and commenced on the cycle ergometry for up to 14 days. In Group B

(control), patients will have standard care and nutrition prescribed by the treating physician and standard physiotherapy as determined by the treating physician.

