6.2. Study Visits and Procedures

a. Screening and Procedures

Patients admitted to SICU NUH will be screened based on inclusion and exclusion criteria within 24 hours of admission. If the patient is sedated, the PIF leaflet will be given to the listed next of kin or the study subject if there are not cognitively impaired. The patient or NOK will be given 24 hours to consider the PIF and to ask any questions before recruitment. Once recruited, randomisation will occur and the patient will be allocated into each treatment arm.

b. Study Visits and Procedures

After recruitment, the patients allocated to group A will undergo baseline quadriceps muscle ultrasound and daily indirect calorimetry measurements while intubated. The measured REE and energy expenditure from CE will be recorded on the patient's notes. The dose of enteral feed will then be prescribed and administered to the patient. If the patient gets extubated during the study period of 14 days, the patient will be fed based on the last

recorded REE measured by the IC with the addition of estimated energy expenditure from the cycle ergometry.

The study subjects will undergo quadriceps ultrasound measurements up to 4x during the study period (twice a week for 14 days). CE will commence daily for 60mins for up to 14 days if there are no temporary cycling exemptions (see 3.4.1) and can be terminated by 3.4.2.

c. Final Study Visit:

Bedside functional outcome measurements will be obtained at ICU discharge and at day 14 of the study.

d. Post Study Follow up.

Bedside functional outcome measurements will be performed on patients at hospital discharge.

e. Discontinuation Visit and Procedures

Subjects may withdraw voluntarily from participation in the study at any time. Subjects may also withdraw voluntarily from receiving the study intervention for any reason. If voluntary withdrawal occurs, the subject will be asked to continue scheduled evaluations, complete an end of study evaluation, and be given appropriate care.

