7.2. Collecting, Recording and Reporting of Serious Adverse Events (SAEs)

1. For Principal Investigator initiated Trials

Previous studies have showed the safety of the cycle ergometry. All ICU and High dependency patients are closely monitored. In the event of any adverse cardiovascular or respiratory events, the cycling can be terminated and the study subject allowed to rest. All SAEs that are unexpected and related to the cycling will be reported. The PI will be responsible for informing DSRB no later than 15 calendar days after first knowledge that the case qualifies for expedited reporting. Follow-information will be actively sought and submitted as it becomes available.

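### ICU mortality is the only mortality outcome: its counting window closes at ICU discharge, so deaths later in the planned follow-up are left out of the comparison between arms

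*Protocol*

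**What the plan says.** Protocol section 2.3 opens its list with: "The secondary outcomes are 1) ICU mortality 2) ICU and hospital length of stay". Functional and strength measures follow. No mortality at a fixed time and no hospital mortality appears in the Protocol.

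The time frame elsewhere is longer than the ICU stay or independent of it:

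- Section 4 has Group A "commenced on the cycle ergometry for up to 14 days", and section 6.2b says "CE will commence daily for 60mins for up to 14 days", subject to the daily exemptions and termination rules.
- Section 6.2b continues energy-based feeding after extubation: "If the patient gets extubated during the study period of 14 days, the patient will be fed based on the last" measured expenditure, with an addition for cycling.
- Section 6.2c names two separate times: "Bedside functional outcome measurements will be obtained at ICU discharge and at day 14 of the study".
- Section 6.2d goes further: "Bedside functional outcome measurements will be performed on patients at hospital discharge".

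On expected benefit, section 2.4a says that patients should "mobilise earlier and avoid problems of prolonged hospital stay". On deaths, section 7.1 requires problems involving local deaths to be reported to the review board within 24 hours, regardless of relatedness.

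**The concern.** ICU mortality counts a death only if it occurs before ICU discharge. The end of that window is not fixed by the design. It differs from patient to patient, it determines ICU length of stay (itself a listed outcome), and it could differ between the arms if the intervention affects recovery. Section 6.1 provides blinding for outcome assessors and does not say that the team deciding on ICU discharge is blinded.

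Two things follow. First, a patient who leaves the ICU on day 7 and dies on day 10 is within the 14-day study period and within follow-up to hospital discharge, yet counts as a survivor in the only mortality outcome. Second, if one arm leaves the ICU sooner, it has fewer days in which a death can count, so ICU mortality can differ between arms even when the risk of death is the same. What is at stake is how the between-arm mortality result can be read in a population of ventilated patients aged 60 or over.

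**Working it through.** The Protocol gives no mortality figure to reproduce. Its sample-size figure (21 per arm, 25 recruited, section 9.1) concerns muscle thickness and does not bear on this point.

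**Step 1: which deaths count.**

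| Time of death | In the section 2.3 mortality outcome? | Within planned follow-up? |
|---|---|---|
| In the ICU | Yes | Yes |
| After ICU discharge, by day 14 | No | Yes (6.2c, day 14) |
| After day 14, in hospital, out of the ICU | No | Yes (6.2d, hospital discharge) |

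**Step 2: can a difference in stay alone move the outcome?** All inputs are assumptions, because the Protocol gives neither a death rate nor an ICU stay. Take the same constant hazard *h* in both arms, in and out of the ICU, and a fixed ICU stay of *L* days in each arm. Then P(death in ICU) = 1 − exp(−*hL*).

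With *h* = 0.015 per day:

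- *L* = 10: 1 − exp(−0.15) = 13.9%
- *L* = 8: 1 − exp(−0.12) = 11.3%
- *L* = 6: 1 − exp(−0.09) = 8.6%

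Against a 10-day stay, the spurious difference is 13.9 − 11.3 = 2.6 points (8-day stay) or 13.9 − 8.6 = 5.3 points (6-day stay). Death by day 14 is 1 − exp(−0.21) = 18.9% in both arms.

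A second assumed set gives the same pattern. Let 25% die by day 28 in both arms, so *h* = −ln(0.75)/28 = 0.01027 per day, with stays of 8 and 12 days. ICU mortality is 1 − exp(−0.0822) = 7.9% against 1 − exp(−0.1233) = 11.6%. Death by day 14 is 1 − exp(−0.1438) = 13.4% in both arms.

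**Step 3: when the distortion vanishes.** The model in step 2 makes discharge unrelated to risk. Suppose instead that the intervention brings forward the discharge only of patients who would have survived anyway. The number of ICU deaths and the number randomised are then unchanged, and the spurious difference is 0.

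**Step 4: scale against chance.** In 25 patients, 2.6 to 5.3 points is 0.65 to 1.3 deaths. Near 12% mortality, the standard error of a difference is √(2 × 0.12 × 0.88 / 25) = 0.092, or about 9 points. Power with 25 per arm (normal approximation, two-sided 5% assumed) is about 16% for 20% against 10%, and 24% for 30% against 15%. A change of time point alone does not cure this.

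**The case against.** ICU mortality is a conventional measure. Here it is one secondary outcome in a pilot whose primary objective is muscle mass, and no conclusion on mortality could rest on 25 patients per arm under any definition. All of that stands, and it limits the weight of the point. It does not make a window that depends on length of stay a good choice when a fixed one costs almost nothing.

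Several stronger readings are tempting, and the documents do not support them:

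- *Later deaths are lost.* They are not. Local deaths are reported under section 7.1, and hospital length of stay and the discharge assessment should make in-hospital vital status known. The deaths are absent only from the between-arm mortality outcome.
- *Cycling continues after ICU discharge wherever the patient is.* The Protocol does not say so. It says up to 14 days and, in section 7.2, "All ICU and High dependency patients are closely monitored". Continuation outside the ICU is an inference, and the point does not need it.
- *The Protocol itself predicts a shorter ICU stay in Group A.* Section 2.4a speaks of prolonged hospital stay. ICU stay is only listed as an outcome, so a difference between arms is possible but not forecast.
- *ICU mortality is the trial's only safety comparison.* Section 2.4b treats safety separately, and tabulation of adverse events by arm is commonly left to a statistical analysis plan, which is not at hand.
- *The trial will show a false survival benefit.* The figures above rest on assumed inputs and on discharge being unrelated to risk. Under another plausible mechanism the distortion is nil.

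**Conclusion.** The point holds as a weakness in how a secondary outcome is defined. It is not a contradiction in the Protocol. The only named mortality outcome stops at ICU discharge, although the study period is up to 14 days and follow-up reaches hospital discharge. Deaths between those times do not enter the mortality comparison, and a difference in ICU stay could by itself shift the result.

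The size cannot be determined from the documents. Under an equal hazard of 1.5% per day and stays of 6 to 10 days, all assumed, the shift is about 3 to 5 percentage points, or roughly one patient per arm. It is zero if only patients who would have survived leave earlier. Importance is minor: it is a cheap improvement in a 50-patient pilot, and mortality remains underpowered whichever definition is used.

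**What to change.** In section 2.3, add death from any cause by a fixed day counted from randomisation, at least day 14 (the Protocol's own study period), and name it as the main mortality comparison. Add it and do not substitute it: replacing ICU mortality outright with day-14 death would drop ICU deaths after day 14, which are now counted. Keep ICU mortality, and add in-hospital mortality, as descriptive outcomes only, because both depend on length of stay.

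The cost is a line in section 2.3 and one case-report-form field for vital status and date of death. Patients still in hospital need no new visit. Those discharged before the chosen day need a record check or a phone call, and a later day means more such calls.

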3.4. Exclusion Criteria

- 1) Unable to follow commands at baseline before hospital admission (e.g. Severe dementia)
- 2) Acute condition where cycling is a contraindication (e.g. leg fracture)
- 3) not expected to survive the subsequent 48 hours
- 4) Body habitus unable to fit the cycle ergometry
- 5) Patients at high risk of refeeding (i.e. NUTRIC score ≥ 5): malnourished patients with anorexia nervosa, chronic malabsorption syndromes, chronic alcoholism, or patients with massive weight loss.
- 6) Extremes of BMI: i.e. BMI < 16 or > 30
- 7) Liver failure
- 8) Cycling exemptions precluding cycling within the first 4 days of mechanical ventilation
- 9) Requirement for inspired oxygen content (FiO₂) greater than 0.8
- 10) Expected to be on renal replacement therapy for longer than 12 hours per session
- 11) PEEP > 15 mmHg
- 12) Air leaks through chest drains
- 13) Palliative goals of care or limitation of treatment established by the CARE form
- 14) Readmissions to ICU

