3.4.1 Temporary cycling exemptions (to be reviewed before daily cycle ergometry sessions)

1. Respiratory
 - a. Persistent O₂ saturation <88%
2. Cardiovascular
 - a. Active myocardial ischemia (MI)
 - b. Unstable or uncontrolled arrhythmia
 - c. Any increase in vasoactive infusions within the last 2 hours
 - d. Mean arterial pressure (MAP) <60 or >110 mmHg within the last 2 hours
 - e. Heart rate (HR) <40 or >140 beats per minute (BPM) within the last 2 hours
3. Receipt of neuromuscular blocking agents within the last 4 hours
4. Uncontrolled pain
5. Severe agitation (Richmond Agitation and Sedation Scale, RASS [48]) >2) within the last 2 hours
6. Change in goals to palliative care
7. Team perception that cycling was not appropriate, despite absence of above exemption criteria

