3.4.2 Indication for the premature termination of cycle ergometry

1. unplanned extubation
2. suspected new unstable or uncontrolled arrhythmia, or suspected myocardial ischaemia
3. ICU physician request to terminate session
4. PT terminated session due to physiologic concerns.
5. Study subject request to terminate session.

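### Section 2.4b promises that a parameter deviation will end cycling, but the stop list in 3.4.2 requires no stop for a change in heart rate, MAP or oxygen saturation

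*Protocol*

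**What the plan says.** Four places in the protocol bear on when a cycling session stops.

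- **Section 2.4b (safety end points)** expects that "Patients might have some mild cardiovascular instability as with any exercise regimen", refers to exclusion criteria applied before exercise begins, and then adds that during monitoring "any deviation from baseline parameters will lead to the termination of the exercise cycle ergometry".
- **Section 3.4.1 (temporary exemptions)** holds the numeric vital-sign limits. Its title says that they are "to be reviewed before daily cycle ergometry sessions". They include "Mean arterial pressure (MAP) <60 or >110 mmHg within the last 2 hours", "Heart rate (HR) <40 or >140 beats per minute (BPM) within the last 2 hours" and persistent oxygen saturation below 88%.
- **Section 3.4.2 (premature termination)** lists five indications: unplanned extubation; "suspected new unstable or uncontrolled arrhythmia, or suspected myocardial ischaemia"; "ICU physician request to terminate session"; termination by the physiotherapist on physiologic grounds; and the subject's own request. Section 6.2b sends the reader to 3.4.1 for starting a session and to 3.4.2 for ending one.
- **Section 7.2 (serious adverse events)** says that cycling may be stopped after an adverse cardiovascular or respiratory event. The wording permits a stop and does not require one.

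**The concern.** Section 2.4b describes an in-session safeguard in mandatory terms: a deviation in a monitored parameter ends the session. The working list contains no such rule. A heart rate above 140 during cycling would have barred the session from starting under 3.4.1. Once the session is running, 3.4.2 requires no stop unless arrhythmia or ischaemia is suspected, or a clinician or the subject decides to stop.

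The participants are at least 60 years old and mechanically ventilated, and consent may come from a legal representative. If staff follow 3.4.2, as is likely, the risk section describes a stricter protection than the one in force. Different staff may also stop at different points, because no in-session limit is written down.

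**Working it through.** The plan gives no figure to reproduce, and the point depends on no power or error-rate calculation. The check sets the texts side by side and counts.

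**1. Is the 2.4b trigger defined anywhere?** The word baseline occurs three times in the protocol: in 2.4b; in 3.4 item 1 ("Unable to follow commands at baseline before hospital admission"); and in 6.2b, for the first quadriceps ultrasound. None of the three defines a vital-sign baseline.

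**2. What does 3.4.2 require?**

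| Item | Type | Numeric limit | Required stop for a change in heart rate, MAP or saturation |
|---|---|---|---|
| 1. Unplanned extubation | event | no | no |
| 2. Suspected arrhythmia or ischaemia | physiologic event | no | no, unless the change is read as one of these |
| 3. Physician request | clinician's decision | no | no |
| 4. Physiotherapist, physiologic concerns | clinician's decision | no | no |
| 5. Subject request | subject's decision | no | no |

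By type: 2 events + 2 clinician decisions + 1 subject decision = 5 items. Items with a numeric limit: 0.

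**3. Where are the numeric limits?** Section 3.4.1 has 1 for saturation (88%) + 2 for MAP (60 and 110 mmHg) + 2 for heart rate (40 and 140 bpm) = 5 limits on 3 parameters. All are reviewed before the session, and the MAP and heart rate limits look back over 2 hours. Neither 3.4.2 nor 6.2b carries them into the session. Section 2.4b also treats the pre-exercise criteria and the in-session stop as separate safeguards.

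**4. Two readings of 2.4b.**

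- *Literal: any change ends the session.* As an illustration with assumed values, heart rate rises from 90 to 105 bpm during cycling. The change is 105 − 90 = 15 bpm, which is a deviation. Yet 40 < 105 < 140, so it is inside the 3.4.1 limits, and by itself it triggers no item of 3.4.2. A rule that stops here would end sessions for an ordinary response to exercise.
- *Sensible: a session stops when a parameter leaves an acceptable range.* The only range in the protocol is in 3.4.1. Staff can stop at those limits through 3.4.2 item 4, but nothing requires them to.

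The first reading is unworkable. On the second, the safeguard is available but not required.

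**The case against.** The strongest reply is that this is loose wording in a narrative section. Section 6.2b names 3.4.1 and 3.4.2 as the working rules and does not mention 2.4b, so staff know which list to use. Section 3.4.2 does address physiology: item 2 is a cardiac trigger, and items 3 and 4 let the physician or physiotherapist stop for any concern. Leaving such stops to clinicians is a legitimate choice in closely monitored patients, and an over-strict 2.4b errs towards stopping.

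Much of this stands, and it rules out three stronger inferences that a reader might draw.

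- *That sessions will be cut short for trivial changes.* The same paragraph of 2.4b expects mild instability with exercise, which undercuts the literal reading. The heart rate illustration shows why that reading fails; it does not predict what staff will do.
- *That staff can satisfy both texts only by stopping at every deviation.* On the sensible reading, stopping at the 3.4.1 limits through item 4 satisfies both.
- *That 3.4.2 lacks physiologic stopping, or that the permissive wording in 6.2b and 7.2 makes its indications optional.* Items 2 to 4 answer the first part. In 6.2b the wording may simply point to the list of grounds, and 7.2 is reporting text.

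What the reply does not remove is the difference between a stop that is promised and a stop that is allowed. Item 4 permits the physiotherapist to act at a heart rate above 140; 2.4b tells the reader that the session will end.

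**Conclusion.** The point holds as a minor inconsistency between the safeguard described in 2.4b and the one required by 3.4.2. Its size can be given only as counts: none of the five stop indications carries a numeric limit, and all five vital-sign limits apply before the session only. The mismatch in wording is certain.

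No effect on delivered sessions can be estimated, because the protocol gives no data on how often parameters move during cycling. A reader might go on to infer a loss of cycling dose or of power; the documents support neither. Nothing is claimed about sample size, feeding or analysis.

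The conclusion assumes that staff work from 3.4.2, as 6.2b directs, and that no separate bedside procedure sets in-session limits. The protocol refers to none.

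**What to change.** 1. Add one indication to 3.4.2: the session is stopped if a 3.4.1 vital-sign limit is crossed during cycling, that is, persistent oxygen saturation <88%, MAP <60 or >110 mmHg, or heart rate <40 or >140 bpm. The 2-hour look-back belongs to the pre-session check and should not be carried over.
2. Keep the existing items, so that the physician and physiotherapist can still stop for other concerns.
3. Reword the 2.4b sentence to say that cycling will be terminated if any indication in 3.4.2 occurs.

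Sections 6.2b and 7.2 are compatible with this and need no change. Rewording 2.4b alone would remove the contradiction, but only by lowering the stated safeguard; the addition to 3.4.2 is what improves protection.

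The cost is a minor amendment for the review board and some sessions ended early. The limits are already in the protocol, and the patients are already monitored.
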